6.11.3 Other Efficacy Endpoints

6.12.1 Adverse Events

Adverse events will be collected from the time of study drug administration through the last day of the subject's participation in the study.

A treatment emergent adverse event (TEAE) is defined as:

- Any AE that has an onset on or after the first dose of study drug, through the last day of the subject's participation in the study
- Any pre-existing AE that has worsened in severity on or after the first dose of study drug, through the last day of the subject's participation in the study

A treatment-related AE is defined as an AE classified by the Investigator as 'Related' to the study drug. If an AE has missing relationship it is assumed to be related to the study drug for analysis purposes.

Maximum severity (Life threatening) will be assumed for an AE with missing severity.

An overall summary table of AE incidence (number and percent of subjects) and number of events, will be presented by treatment group and overall, for the following categories:

- Any TEAE
- Treatment-Related TEAEs
- Serious TEAEs
- Serious Treatment-Related TEAEs
- TEAEs Leading to Study Drug Discontinuation
- TEAEs Leading to Early Withdrawal
- TEAEs Leading to Death

Summaries of TEAE incidence and number of events by SOC and PT will be presented by treatment group and overall, for the following:

- TEAEs
- Treatment-related TEAEs
- Serious TEAEs
- Serious Treatment-Related TEAEs
- TEAEs Leading to Study Drug Discontinuation
- TEAEs by Maximum Severity, (incidence only)

• Treatment-Related TEAEs by Maximum Severity, (incidence only)

The following listings of AEs will be presented in Section 14.3.2 of the CSR:

- Serious AEs
- AEs Leading to Early Withdrawal
- AEs Leading to Death

AE tabulations will be presented by SOC and PT in descending overall frequency of AE incidence and then alphabetically for ties.

All reported AEs will be listed in Appendix 16.2.7 of the CSR.

6.12.2 Laboratory Data

Descriptive statistics for the observed values and change from baseline will be presented by treatment group and visit for each hematology, urinalysis, and serum chemistry (including triglycerides and thyroid panel) parameter. Each continuous measurement will be classified as below, within, or above normal range, based on ranges supplied by the laboratory used. Categorical parameters may also be classified as normal or abnormal based on normal ranges, and subject counts within each category will be summarized. Shift tables in relation to the normal range from baseline to each post-baseline visit will be presented.

Summaries and listings will be presented using the original unit for each parameter as received from the analytical laboratory.

A listing of out of normal range laboratory values throughout the study will be presented. All laboratory assessments, including urine pregnancy tests, drug tests, and serology will also be listed.

A separate listing will be provided for all Alanine Aminotransferase (ALT), Aspartate Aminotransferase (AST), and Bilirubin results at all timepoints for any subjects who meet the criteria for liver function abnormalities as defined in Section 6.2.25.

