# 7. SELECTION AND WITHDRAWAL OF SUBJECTS

### 7.1. Subject Inclusion Criteria

#### **Inclusion Criteria: Screening**

Subjects must meet ALL the following criteria to be enrolled in this study:

- 1. An Institutional Review Board (IRB) approved written informed consent and privacy language (Health Insurance Portability and Accountability Act (HIPAA)) authorization must be obtained from the subject prior to performing any study -related procedures.
- 2. Consent to being included in a research subject database.
- 3. Subject is  $\geq 18$  and  $\leq 75$  years of age.
- 4. Diagnosis of Type 2 Diabetes.
- 5. At least moderate pain intensity over the last week as assessed by PGI-S at Visit 1.
- 6. Hemoglobin A1c (HbA1c)  $\leq 11\%$  (measured at Visit 1).
- 7. Stable use of diabetic medications beginning 1 month prior to Visit 1 (adequate glycemic control with diet and exercise alone is also permitted).
- 8. Diabetic peripheral neuropathy, of symmetrical nature and in lower extremities for ≥4 years (DPN in the upper extremities is not exclusionary).

- 9. Presence of pain due to diabetic neuropathy for at least 6 months prior to screening.
- 10. Total score of  $\geq$ 4 on the Michigan Neuropathy Screening Instrument.
- 11. Body mass index  $\leq 40 \text{ kg/m}^2$ .
- 12. Absence of impaired hepatic function. Impaired hepatic function is characterized by a previous known diagnosis of chronic liver disease, and/or abnormal serum total bilirubin (TBL), or alanine transaminase (ALT), aspartate transaminase (AST), or alkaline phosphatase (ALP)>1.5x upper limit of normal (ULN) at screening.
- 13. Calculated creatinine clearance  $\geq 60$  mL/minute (Cockcroft-Gault formula).
- 14. Fasting triglycerides  $\leq 600 \text{ mg/dL}$ .
- 15. Except as noted in criteria 12-14 above, clinical laboratory values must be within normal limits, or deemed not clinically significant by the Investigator.
- 16. Female subjects of child bearing potential with a negative pregnancy test prior to entry into the study and who are practicing a highly effective method of birth control (e.g., oral or parenteral contraceptives, intrauterine device, barrier [condom and spermicide], abstinence) and who do not plan to become pregnant, breastfeed, or donate ova during the course of the study and for 28 days after the final administration of investigational product.

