### 9.4. Safety and Pharmacovigilance

#### 9.4.1. Adverse Events – Relationship to Study Drug

An adverse event is any untoward, undesired, unplanned clinical event in the form of signs, symptoms, disease, or laboratory or physiological observations occurring in a human being participating in a clinical study with an Aptinyx study drug, regardless of causal relationship.

Laboratory abnormalities are not considered adverse events unless they are associated with clinical signs or symptoms or require medical intervention. However, a laboratory abnormality (e.g., a clinically significant change detected on clinical chemistry, hematology, or urinalysis results) that is independent from the underlying medical condition and that requires medical or surgical intervention, or leads to study drug interruption or discontinuation, must be considered an adverse event.

The causality of each AE should be assessed and classified by the Investigator as "related" or "not related." An adverse event is considered related if there is a reasonable possibility that the event may have been caused by the study drug under investigation (i.e., there are facts, evidence, or arguments to suggest possible causation). There is also a timely relationship to the administration of the investigational drug and the event follows a known pattern of response for which no alternative cause is present.

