# 11. STOPPING CRITERIA

Subjects will be withdrawn from the treatment period of the study if any of the following laboratory results and symptoms are observed.

- ALT or AST >8xULN Discontinue subject treatment immediately.
- ALT or AST >5xULN

ALT or AST >3xULN and (TBL >2xULN or INR >1.5)

Discontinue treatment if result is confirmed upon retest (to be done within 48 hours or as soon as feasible).

- ALT or AST >3xULN with the appearance of fatigue, nausea, vomiting, right upper quadrant pain or tenderness, fever, rash, and/or eosinophilia (>5%)
- ALT or AST >3xULN that persists for  $\geq$  4 weeks

If an increase of serum aminotransferase of >3xULN is identified, repeat testing within 48 to 72 hours of all four of the usual serum measures (ALT, AST, ALP, and TBL) should conducted to confirm the abnormalities and to determine if they are increasing or decreasing.

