6.2.25 Liver Function Abnormalities

Any subject meeting the following criteria will be identified and results will be listed separately for these subjects:

ALT or AST >3xULN or Bilirubin >2xULN

Where ALT = Alanine Aminotransferase, AST = Aspartate Aminotransferase, and ULN = Upper Limits of Normal.

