14.3.5.2	Compliance with Study Drug - Safety Population	IP	
14.3.6	Vital Signs and Physical Examination	IP	
14.3.6.1	Vital Signs, Change from Baseline - Safety Population	IP	
14.3.6.2	Electrocardiogram Results, Change from Baseline - Safety Population	IP	
14.3.6.3	Electrocardiogram Results, Shift in Overall Interpretation - Safety Population	IP	
14.3.7	Other Safety	IP	
14.3.7.1	Hematology Data, Descriptive Statistics - Safety Population	IP	
14.3.7.2	Hematology Data, Normal Range Shifts - Safety Population	IP	
14.3.7.3	Serum Chemistry Data, Descriptive Statistics - Safety Population	IP	14.3.7.1
14.3.7.4	Serum Chemistry Data, Normal Range Shifts - Safety Population	IP	14.3.7.2
14.3.7.5	Coagulation Data, Descriptive Statistics - Safety Population	IP	14.3.7.1
14.3.7.6	Coagulation Data, Normal Range Shifts - Safety Population	IP	14.3.7.2
14.3.7.7	Urinalysis Data, Descriptive Statistics - Safety Population	IP	
14.3.7.8	Urinalysis Data, Normal Range Shifts - Safety Population	IP	14.3.7.2
14.3.7.9	Sheehan-Suicidality Tracking Scale, Change from Baseline - Safety Population	IP	

14.3.8.1	Concomitants Medications by ATC Level 3 and Preferred Name	IP	
	- Safety Population		

Figure Number	Figure Title	Validation Method	Shell Number (If Repeat)
14.2.1.1	Average Pain Intensity Related to DPN, Change from Baseline in Weekly Mean NRS Score, LS Mean (95% CI) - Line Plot - Modified Intent-to-Treat Population	MR	
14.2.1.2	Average Pain Intensity Upon Walking, Change from Baseline in Weekly Mean NRS Score, LS Mean (95% CI) - Line Plot - Modified Intent-to-Treat Population	MR	
14.2.1.3	Worst Pain Intensity Related to DPN, Change from Baseline in Weekly Mean NRS Score, LS Mean (95% CI) - Line Plot - Modified Intent-to-Treat Population	MR	
14.2.1.4	Average Pain Intensity Related to DPN, Cumulative Response (Percent Reduction from Baseline) in the Weekly Mean NRS Score at Week 12 - Modified Intent-to-Treat Population	MR	
14.2.1.5	Average Pain Intensity Related to DPN, Time to First ≥30% Reduction (Days) in Mean NRS Score - Modified Intent-to-Treat Population	MR	14.2.1.4
14.2.1.6	Average Pain Intensity Related to DPN, Time to First ≥50% Reduction (Days) in Mean NRS Score - Modified Intent-to-Treat Population	MR	14.2.1.4
14.2.1.7	Average Pain Intensity Related to DPN, LS Mean Difference in Weekly Mean NRS Score at Week 12, Exploratory Analyses - Forest Plot - Modified Intent-to-Treat Population	MR	

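### No planned table counts, by arm, the subjects whose liver tests cross the protocol's own Section 11 multiples of ULN

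*SAP*

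**What the plan says.** SAP 6.12.2 plans these laboratory outputs:

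- Summary statistics: "Descriptive statistics for the observed values and change from baseline will be presented by treatment group and visit". Under SAP 6.3.4 these are n, mean, median, SD, minimum and maximum.
- A three-level classification: "Each continuous measurement will be classified as below, within, or above normal range, based on ranges supplied by the laboratory used".
- Shifts on those three levels: "Shift tables in relation to the normal range from baseline to each post-baseline visit will be presented". In SAP Section 11 this is Table 14.3.7.4, "Serum Chemistry Data, Normal Range Shifts - Safety Population".
- Listings of all laboratory results and of out-of-range values.
- A separate listing of ALT, AST and bilirubin at all timepoints for subjects meeting SAP 6.2.25, that is ALT or AST >3xULN or bilirubin >2xULN: "Any subject meeting the following criteria will be identified and results will be listed separately for these subjects". It is display 14.3.4.1.

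Protocol Section 11 works with finer steps. It uses >3xULN with symptoms, >3xULN lasting at least 4 weeks, >3xULN combined with total bilirubin >2xULN or INR >1.5, >5xULN, and "ALT or AST >8xULN Discontinue subject treatment immediately". Protocol 9.4.1 states: "Laboratory abnormalities are not considered adverse events unless they are associated with clinical signs or symptoms or require medical intervention". The same section makes an abnormality an adverse event when it leads to interruption or discontinuation of study drug.

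**The concern.** Safety and tolerability are part of the primary objective, and the liver has prior findings in these documents. Protocol Section 4 reports adverse liver changes in dogs at 240 mg/kg/day and names increased ALT among the most common TEAEs. It also describes one subject in study 2001 whose ALT and AST met stopping criteria, and one in study 2002 with raised GGT, ALT and AST in the 200 mg period.

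The natural question for the report is how many subjects in each arm passed 3, 5 or 8xULN, and how many had raised transaminases together with raised bilirubin. No planned table answers it. The shift table cannot grade a rise, the summary statistics do not count subjects, and the only output that uses ULN multiples is a subject listing with no n/N by arm.

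**Working it through.** The plan gives no figure to reproduce here. The check applies the SAP's rules to example values. All xULN values below are assumed for illustration.

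**Step 1. The shift rule (SAP 6.12.2) beside the listing rule (SAP 6.2.25).** A value above 1xULN is above normal.

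| Baseline to post-baseline (xULN) | Categories | Shift table | Listed (>3xULN) |
|---|---|---|---|
| 0.8 to 1.1 | within to above | shift | no |
| 0.8 to 4 | within to above | same shift | yes |
| 1.2 to 3.5 | above to above | no shift | yes |
| 1.5 to 1.6 | above to above | no shift | no |
| 1.5 to 8.1 | above to above | no shift | yes |

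The shift table does not separate row 1 from row 2, or rows 3 to 5 from one another. The listing does.

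**Step 2. Can baseline be above normal?** Inclusion criterion 12 (Protocol 7.1) ends with "ALP)>1.5x upper limit of normal (ULN) at screening". If the 1.5 multiple covers ALT and AST, entry at up to 1.5xULN is allowed. The wording could also be read as attaching the multiple to ALP only. The limit applies at screening, while baseline is the last value before first dose (SAP 6.2.2), so the two can differ. Rows 1 and 2 do not depend on this.

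**Step 3. What the mean shows.** With 204 subjects at 1:1, each arm has 204/2 = 102. At 15% drop-out about 102 × 0.85 = 87 remain. One subject moves the arm's mean change by (post − baseline)/n:

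- 1.2 to 3.5xULN: 2.3/102 = 0.023xULN, or 2.3/87 = 0.026xULN.
- 1.5 to 8.1xULN: 6.6/102 = 0.065xULN, or 6.6/87 = 0.076xULN.

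The maximum would show the highest value at that visit, but it is the same whether one subject or several reached it.

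**Step 4. Retests.** Section 11 asks for repeat tests within 48 to 72 hours of a rise above 3xULN. After a Week 4 visit on Day 28, that means Day 30 or 31. SAP 6.2.12 and 6.2.13 map Days 2 to 42 to Week 4 and rank unscheduled results last. If Day 28 shows 3.2xULN and the retest 4.5xULN, the by-visit summary uses 3.2. The retest reaches the listing only.

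**Step 5. Which rises reach the AE tables?** Under Section 11, >8xULN and confirmed >5xULN lead to discontinuation. Under Protocol 9.4.1 they are then adverse events, and they appear by arm in Table 14.3.1.6. A rise of >3 to 5xULN need not stop drug if it has no listed symptoms, no raised bilirubin or INR, and lasts under 4 weeks. Without intervention or interruption of drug, it need not be an adverse event.

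**Step 6. The combined criterion.** SAP 6.2.25 joins its conditions with *or*. Subjects with both raised ALT/AST and raised bilirubin are inside the listing but are not flagged or counted.

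**The case against.** A reader might infer that liver tests are compared between arms only as below, within or above normal, and that hepatic signals by arm are lost. The documents do not support that.

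- SAP 6.12.2 also gives statistics by arm and visit. With SD and maximum among them, a few large rises in the values used would be visible.
- The listing shows every ALT, AST and bilirubin result for each flagged subject. SAP 6.3.6 sorts listings by treatment group first, so arm counts can be made by hand in a trial of this size.
- The most alarming case, a rise past 8xULN, must stop drug, becomes an adverse event and is counted by arm among TEAEs leading to discontinuation. Confirmed rises above 5xULN follow the same route.
- SAP Section 6 allows further tables in the report if the data warrant them.

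The background is also milder than a selective reading suggests. Protocol Section 4 calls the notable laboratory results in study 2001 generally comparable across groups. It puts exposure at the dog NOAEL at about 70-fold that of the 50 mg dose. Nor can one say that this is the first 12-week exposure: Section 4 mentions an ongoing fibromyalgia study without giving its length.

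All of this stands. It narrows the point but does not remove it. A maximum and an SD are not counts, a listing is not a comparison, and a table added after the data are seen is weaker than one planned beforehand.

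**Conclusion.** The point holds as a missing summary table, not as missing data. No planned table compares the arms at the Section 11 multiples or on raised ALT/AST together with raised bilirubin. It matters mainly for symptom-free rises of >3 to 5xULN that do not affect dosing, and for peaks found only at a retest.

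The documents give no expected frequency for such rises, so the effect cannot be put as a number of subjects. In an arm of 102, each such subject is 1/102 = 1.0%, a proportion that no planned table reports. All safety analyses are descriptive (Protocol 12.7), so no test or error rate is affected. The part about subjects already above normal at baseline rests on the broader reading of inclusion criterion 12, or on change between screening and baseline. The rest does not. This is a cheap improvement.

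**What to change.** Add one table to SAP 6.12.2 and SAP Section 11 for ALT, AST and total bilirubin: baseline category against worst post-baseline category, by arm, with n/N (%), in the Safety Population.

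- ALT and AST: <=1, >1-3, >3-5, >5-8 and >8xULN.
- Bilirubin: <=1, >1-2 and >2xULN.
- One further row: subjects with ALT or AST >3xULN together with bilirubin >2xULN. State whether both must come from the same blood sample.

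Take the worst value over all scheduled, early-withdrawal and unscheduled results, and say that the precedence rule in SAP 6.2.13 does not apply to this table. Section 11 also accepts INR >1.5 in place of raised bilirubin, but Protocol 9.3.5 names no INR among the laboratory tests. A footnote can report INR where it was measured. Keep the 14.3.4.1 listing.

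The cost is a short SAP addition and one more descriptive table to program. It needs no new data and changes no clinical rule.

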6.12.3 Vital Signs

Descriptive statistics for observed values and changes from baseline in the following vital signs will be tabulated at each post-baseline visit:

Systolic blood pressure (mmHg)

- Diastolic blood pressure (mmHg)
- Pulse rate (bpm)
- Body weight (kg)

All vital signs measurements throughout the study will be listed.

6.12.4 Physical Examination

All physical examination collection data (including brief physical examination) will be listed.

6.12.5 Electrocardiogram Data

Descriptive statistics for observed values and changes from baseline in the following ECG variables will be tabulated at each post-baseline visit:

- Heart rate (bpm)
- PR interval (ms)
- RR interval (ms)
- QRS complex (ms)
- QT interval (ms)
- QTc interval (ms) [Bazett's formula QTcB]
- QTc interval (ms) [Fridericia's formula QTcF]

Shift tables in relation to the overall interpretation (Normal, Abnormal Not Clinically Significant [NCS], and Abnormal Clinically Significant [CS]) from baseline to each post-baseline visit will be presented.

All ECG assessments throughout the study will be listed.

6.12.6 Sheehan-Suicidality Tracking Scale

Descriptive statistics for observed and change from baseline S-STS total score will be summarized by treatment group for each post-baseline visit.

All S-STS responses throughout the study will be listed.

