- 13. Sensitivity to, allergy to, or concomitant use of *N*-methyl-D-aspartate receptor ligands including ketamine, esketamine, amantadine, dextromethorphan, memantine, methadone, dextropropoxyphene, lamotrigine, and/or ketobemidone.
- 14. Use of NMDAR-binding drugs (e.g., ketamine, esketamine, amantadine, dextromethorphan, memantine, methadone, dextropropoxyphene, lamotrigine, and/or ketobemidone) within 30 days prior to dosing or during the study. Use of high concentration capsaicin patch within 3 months prior to screening; use of lidocaine patch within 1 month prior to screening.
- 15. Sensitivity to or intolerance to acetaminophen or associated formulation components.
- 16. Hypersensitivity or intolerance to multiple medications, in the opinion of the investigator.
- 17. Amputations of lower extremities (toe(s) amputation is allowed).
- 18. Meets the criteria for suicidal intent, plan and/or behavior by scoring 3 or 4 on Questions 2 or 13, or 2 or higher on any Question 1a (only if 1b is coded YES), 3, 4, 5, 6, 7, 8, 9, 10, 11, 12, or 14 based on the S-STS or who is at significant risk to commit suicide, as assessed by the investigator, at Visit 1 or Visit 2.
- 19. Planned surgery during study participation.
- 20. Active malignancy or a history of malignancy (except for treated non-melanoma in-situ skin cancer) within 5 years of screening.
- 21. Employee, contractor, or volunteer of the study site, CRO, or Aptinyx, or relative of any employee, contractor, or volunteer of the study site, CRO, or Aptinyx.
- 22. Any condition, including serious medical conditions, that could interfere with the ability of the subject to participate in the study or could confound study assessments. Presence of an exclusionary masquerading disorder in the Masquerading Disorders Tool (MDT) assessment.
- 23. Subject has evidence of any clinically significant, uncontrolled gastrointestinal, endocrinologic, hematologic, immunologic, metabolic, urologic, pulmonary (including uncontrolled, obstructive sleep apnea), neurologic, dermatologic, and/or other major disease (exclusive of diabetes) that may interfere with study participation, as assessed the investigator.

- 24. Previous randomization in current or previous NYX-2925 clinical trials.
- 25. Subject has filed for a disability claim or has any pending worker's compensation litigation.

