#### 12.7.5. Suicidal Ideation

Subjects with suicidal ideation or behavior will be identified with the S-STS.

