3.3 Other Efficacy Endpoints

3.4 Safety Endpoints

The safety endpoints will include adverse events (AE), serious adverse events (SAE), discontinuation due to AE and the S-STS.

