6.2.24 Sheehan-Suicidality Tracking Scale

The standard version of the Sheehan-Suicidality Tracking Scale (S-STS) is a 16-item scale that assesses the seriousness of suicidality phenomena on a Likert-type scale (0 to 4; where 0 corresponds to "not at all" and 4 corresponds to "extremely"). It also assesses the frequency of key phenomena and the overall time spent in suicidality. The total S-STS score is obtained by summing the responses to:

- question 1a (only if the answer to question 1b: did you intend to die as a result of any accident? is "Yes")
- questions 2 to 11
- max of responses to question 12 or any row of question 16
- max of responses to question 14 or any row of question 15

Question 1a: how seriously did you plan or intend to hurt yourself in any accident, either by not avoiding a risk or by causing the accident on purpose?

Question 2: think (even momentarily) that you would be better off dead, need to be dead or wish you were dead?

Question 3: think (even momentarily) about harming or hurting or injuring yourself—with at least some intent or awareness that you might die as a result—or think about suicide (killing yourself)?

Question 4: have a voice or voices telling you to kill yourself or have dreams with any suicidal content?

Question 5: have any suicide method in mind (i.e., how)?

Question 6: have any suicide means in mind (i.e., with what)?

Question 7: have any place in mind to attempt suicide (i.e., where)?

Question 8: have any date / timeframe in mind to attempt suicide (i.e., when)?

Question 9: intend to act on thoughts of killing yourself?

Question 10: intend to die as a result of a suicidal act?

Question 11: feel the need or impulse to kill yourself or to plan to kill yourself sooner rather than later?

Question 12: take active steps to prepare for a suicide attempt in which you expected or intended to die (include anything done or purposely not done that put you closer to making a suicide attempt)?

Question 14: attempt suicide (try to kill yourself)?

Question 15: Since your last visit, how many times did you attempt suicide?

Question 16: Since your last visit, how many times did you take active steps to prepare for a suicide attempt in which you expected or intended to die (include anything done or purposely not done that put you closer to making a suicide attempt)?

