16.2.6.2	Average Pain Intensity Upon Walking in the Past 24 Hours, Weekly Mean NRS Score - Modified Intent-to-Treat Population	IP	16.2.6.1

16.2.6.4 Daily Rescue Medication (Acetaminophen 500 mg) Usage - Modified Intent-to-Treat Population IP 16.2.6.5 Daily Sleep Interference Scale - Modified Intent-to-Treat Population IP 16.2.6.6 Pain Catastrophizing Scale - Modified Intent-to-Treat Population IP 16.2.6.7 Brief Pain Inventory for Diabetic Peripheral Neuropathy - Modified Intent-to-Treat Population IP 16.2.6.8 Norfolk Quality of Life Questionnaire - Diabetic Neuropathy - Modified Intent-to-Treat Population IP 16.2.6.9 Patient Global Impression of Severity - Modified Intent-to-Treat Population IP 16.2.6.10 Patient Global Impression of Change - Modified Intent-to-Treat Population IP 16.2.6.11 Sheehan-Suicidality Tracking Scale - Modified Intent-to-Treat Population IP 16.2.6.12 Average Pain Intensity Related to DPN, Time to First ≥30% or ≥50% Reduction (Days) in Mean NRS Score - Modified Intent-to-Treat Population IP 16.2.7 Adverse Event Listings IP 16.2.7.1 Adverse Event Data - Safety Population IP	16.2.6.3	Worst Pain Intensity Related to DPN in the Past 24 Hours, Weekly Mean NRS Score - Modified Intent-to-Treat Population	IP	16.2.6.1
16.2.6.5 Daily Sleep Interference Scale - Modified Intent-to-Treat Population 16.2.6.6 Pain Catastrophizing Scale - Modified Intent-to-Treat Population IP	16.2.6.4	Daily Rescue Medication (Acetaminophen 500 mg) Usage -	IP	

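### The S-STS is a named safety endpoint, but no SAP table counts subjects with post-baseline suicidal ideation or behavior, and its listing is limited to mITT

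*SAP*

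**What the plan says.** SAP 3.4 names the scale as an endpoint: "The safety endpoints will include adverse events (AE), serious adverse events (SAE), discontinuation due to AE and the S-STS". Protocol 5.3.3 does the same. Protocol 12.7.5 states its purpose: "Subjects with suicidal ideation or behavior will be identified with the S-STS".

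SAP 6.12.6 plans one summary, at each visit after baseline: "Descriptive statistics for observed and change from baseline S-STS total score will be summarized by treatment group". The index in SAP 11 shows it as table 14.3.7.9, on the Safety Population. SAP 6.3.4 defines the statistics for a continuous variable as n, mean, median, SD, minimum and maximum. SAP 6.12.6 then adds: "All S-STS responses throughout the study will be listed". The index entry for that listing reads "16.2.6.11 Sheehan-Suicidality Tracking Scale - Modified Intent-to-Treat Population".

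SAP 6.2.24 builds the total from Question 1a (only if 1b is Yes), Questions 2 to 11, the larger of Question 12 and any row of Question 16, and the "max of responses to question 14 or any row of question 15". Question 13 appears in none of these. Exclusion criterion 18 (Protocol 7.2) does use it: one way to be excluded is "scoring 3 or 4 on Questions 2 or 13".

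SAP 6.2.12 and 6.2.13 map early-withdrawal and unscheduled assessments to visit windows. If the window already holds a scheduled assessment, that one is analyzed and the early-withdrawal assessment is only listed. Unscheduled assessments rank last. Protocol 9.3.6 separately requires suicidality found after baseline to be recorded as an adverse event.

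**The concern.** A suicidality scale is collected to answer a simple safety question: how many subjects in each arm developed ideation or behavior? Descriptive statistics of a total do not answer it. Such events are expected to be few, so the mean hardly moves and the median stays at zero. Because criterion 18 admits low non-zero scores, falls in some subjects can offset rises in others.

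Three details make the gap wider. The windowing rule can remove a positive assessment from the table, and an early-termination visit is one place where a positive score may appear. The listing, which should be the backstop, covers a smaller population than the table. And an item that can bar a subject from entry cannot change the reported total. At stake is whether a reader of the study report can get a per-arm count from the S-STS itself.

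**Working it through.** **1. Arm size.** SAP 4 gives a difference of 0.73, SD 1.7, two-sided alpha 0.05, power of about 80% and 15% drop-out. SAP 5 gives 1:1 allocation. n per arm = 2 × (1.7/0.73)² × (1.960 + 0.842)² = 85.1, so 86. For drop-out, 86/0.85 = 101.2, so 102 per arm and 204 in total. This reproduces the planned 204, and 102 is used below. The S-STS sections state no figure of their own.

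**2. What the planned statistics show.** Suppose k subjects in an arm have a new total of s and all others change by 0. The mean change is k × s/102. The values of k and s are assumptions.

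| Scenario in one arm | Mean change | Median | Maximum change | Count a subject table would give |
|---|---|---|---|---|
| 1 new score of 4 | 4/102 = 0.04 | 0 | 4 | 1 (1.0%) |
| 1 new score of 8 | 8/102 = 0.08 | 0 | 8 | 1 (1.0%) |
| 1 new score of 16 | 16/102 = 0.16 | 0 | 16 | 1 (1.0%) |
| 3 new scores of 8 | 24/102 = 0.24 | 0 | 8 | 3 (2.9%) |
| 2 rise by 4, 4 fall by 2 | (8 − 8)/102 = 0 | 0 | 4 | 2 (2.0%) |

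One case and three cases scoring 8 have the same median and the same maximum. The last row has a mean change of exactly 0 with two new cases, although the maximum still reads 4. SAP 6.3.5 gives total scores no decimals and means one more, so 0.04 would print as 0.0 and 0.08 as 0.1. If 87 subjects per arm are assessed at a visit, one new score of 8 gives 8/87 = 0.09. The total can reach 4 + 10 × 4 + 4 + 4 = 52 if the rows of Questions 15 and 16 are scored 0 to 4. The SAP words those two questions as numbers of times, so this range is an assumption.

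**3. Windowing.** The S-STS windows in SAP 6.2.12 are Days 2–21 (Week 2), 22–42 (Week 4), 43–70 (Week 8) and 71 onward (Week 12). Take a subject with a clean Week 8 visit on Day 56 who terminates on Day 65 with a positive S-STS. Day 65 maps to Week 8, which is already filled, so the positive result enters no statistic in the table, the maximum included. With visits on Days 14, 28 and 56, the days affected are 15–21 (7), 29–42 (14) and 57–70 (14). That is 35 of the 84 treatment days. It counts days and is not a probability of the event.

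**4. Listing against table.** SAP 6.1.4 defines mITT as the Safety Population with at least one post-baseline pain NRS. A dosed subject with none can be in table 14.3.7.9 but not in listing 16.2.6.11, which contradicts the promise in 6.12.6. This gap and the one in step 3 mostly affect different subjects: the Day 65 subject would normally have diary entries and so remain listed.

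**5. Question 13.** If a subject's only post-baseline finding is on Question 13, the total and its change are both 0, whatever the score on that item.

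**The case against.** The best defense is that cases have several routes into the report. The table gives the maximum by arm and visit, so a case that raises the total is visible in most settings. The table is on the Safety Population. Item responses are listed. Protocol 9.3.6 makes the recording of post-baseline suicidality as an adverse event an instruction, and SAP 6.12.1 then gives number and percent of subjects per arm by system organ class and preferred term, with every event listed. Protocol 12.7.5 says that subjects will be identified, and it does not promise an incidence table. Pain scores are entered nightly from baseline, so few dosed subjects should lack a post-baseline NRS.

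Most of this stands. A reader might infer that the S-STS is reported by means alone and that cases are averaged away or left out of the report. The documents do not support that, because of the maximum, the listing and the adverse event route. Nor is the missing count an undeclared departure from Protocol 12.7.5.

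Three things remain. A maximum is not a count, and under the windowing rule it can miss a case. The adverse event route gives no S-STS-based count: Protocol 9.3.6 sets no score at which a response becomes an event, the tables split by preferred term, and no reconciliation with the S-STS is planned. The listing label still contradicts SAP 6.12.6.

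**Conclusion.** The concern holds in a limited form. The plan summarizes a named safety endpoint by its total score and yields no S-STS-based number of affected subjects per arm. One new score of 8 among 102 moves the mean change by 0.08. One case and three cases with that score share the same median and maximum. A positive early-termination S-STS can be absent from the table altogether. The mITT label is a plain inconsistency with probably small reach, and the documents give no number for the subjects affected.

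A reader might also infer that leaving Question 13 out of the total is a scoring error. The documents give neither its text nor the instrument's scoring rule, so this cannot be concluded. They show only that the item counts for eligibility and not in the reported total.

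The sizes rest on planned enrollment, assumed scores, no change in the other subjects except in the offset row, and visits on nominal days. This is a worthwhile reporting improvement. It does not touch the efficacy analysis, and it does not show that the safety endpoint fails.

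**What to change.** - In SAP 6.12.6, add one descriptive Safety Population table by arm. It should give n (%) of subjects with any post-baseline ideation item above 0, any behavior item above 0 (Questions 12, 14, 15 and 16), Question 13 above 0, and new or worsened findings versus baseline. State in SAP 6.2.24 which items form the ideation group.
- Base these counts on all post-baseline assessments, including early-termination and unscheduled ones, so that the windowing rule does not apply to them.
- Keep table 14.3.7.9 as supportive.
- In SAP 11, change listing 16.2.6.11 from mITT to the Safety Population.

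The cost is one extra table and one changed label. The data are already collected, so there is no added site work and no protocol amendment. The item-level count is useful whether or not Question 13 belongs in the total.
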